Assessing the Effectiveness of Self- and Clinician-administered Crisis Response Planning for Suicide Risk

NCT Number: 2020B0414-B

Date: 5/18/2021

Assessing the Effectiveness of Self- and Clinician-administered Crisis Response Planning for Suicide Risk

1. Objectives

The aim of the current project is to compare the use and preliminary effectiveness of a self-administered version of the Crisis Response Plan (CRP) in decreasing suicidal/death ideation and distress and increasing positive affect when compared to a clinician-administered version of the protocol in a sample of 150 military Veterans experiencing current death or suicidal ideation. As the aim of examining the effectiveness self- and clinician-administered versions of the CRP is exploratory, no hypotheses are proposed. However, the results of this research will inform best practices for administration of the CRP in future research and clinical contexts.

2. Background and Rationale

In response to enhanced detection of suicide risk, there is a need to identify psychotherapeutic interventions targeting suicide risk among military veterans who may be unable or unwilling to seek follow-up mental health services. Indeed, reasons for refusal to seek mental health services among veterans include public and self-stigma (Held & Owens, 2013), adherence to masculine norms (Burns & Mahalik, 2011). However, Wilson et al. (2008) observed that the majority of Army soldiers who were unwilling to speak to a clinician about mental health care were willing to utilize technology-based approaches to mental health care.

2.1 Crisis Response Planning for Suicide Risk. Crisis Response Planning (CRP) is a brief, psychotherapeutic intervention with demonstrated efficacy in increasing positive affect, decreasing negative affect and psychiatric hospitalizations, and reducing suicide attempts by 76% in military personnel when compared to contracts to safety (Bryan et al., 2017, 2018). Given the efficacy and flexibility of the intervention, CRP has been successfully implemented as part of interventions targeting PTSD and suicide risk (Bryan and Rudd, 2018; Rozek & Bryan, 2020). **This proposed research is aimed at examining the efficacy of the intervention in reducing suicidal ideation, distress, and negative affect and increasing positive affect when compared to a self-administered version.**

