CRP is focused on creating personalized set of steps for individuals to follow in case of a crisis and includes individuals' personal warning signs of distress, behavioral coping strategies, reasons for living, social supports to contact, and contact information for professional services, including emergency services. Personalization of the CRP is encouraged, and individuals are instructed to handwrite each step of the CRP on an index card. Additionally, clinicians instruct patients to review the CRP periodically in order to mentally rehearse each step and change the contact of the CRP as needed (e.g., after using the CRP, a behavioral coping strategy was found to be unhelpful or iatrogenic).

3. Procedures

3.1. Research Design. A two-arm randomized controlled simulation design will be employed in both parts of this proposed research. Participants will be randomized using stratified blocks of 6 or 8 participants, per recommendations by Krenan et al. (1999), based on gender and suicide attempt history (no history of suicide attempts, history of one suicide attempt, or history of multiple suicide attempts).

3.2. Sample. A sample of 150 Veterans will be included in the study and randomized to study conditions (75 in the clinician-administered CRP condition and 75 in the self-administered CRP condition). Results of a priori power analyses conducted using G*Power software (Faul et al., 2007)

indicate that a total sample of 150 will results in a highly-powered study ($\beta = .98-.99$) to detect medium-sized effects in all regression-based analyses, assuming moderate correlations amongst the seven daily measurements for this proposed study. Therefore, although we anticipate low attrition from this study, the proposed sample size is sufficiently powered for the proposed analyses, even when conservatively assuming a 20% attrition rate observed in longitudinal efficacy trials of the CRP (Bryan et al., 2017). Online recruitment methods for the study are include web-based survey and research recruitment systems (e.g., SurveyMonkey), listservs and forums, and social media sites (e.g., Facebook, Twitter, Reddit). Additionally, we are requesting use of ResearchMatch (RM), which is an NIH sponsored national registry for research volunteers. ResearchMatch (RM) and OSU have had a fully executed agreement since August 2009. The IRB of record for ResearchMatch is Vanderbilt University. The Principal Investigator will be authorized to recruit study participants.

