3.7. Internal Validity. A number of measures will be implemented to mitigate threats to internal and external validity. Specifically, the randomization procedures employed in the proposed research study (See Section 4.1.2) were selected to account for the potential influences of gender and suicide attempt status on study findings. Further, all study personnel administering the CRP will be trained to administer the protocol to maintain an average fidelity rating of 85%. A random selection of CRP sessions recorded using Zoom teleconferencing software, will be reviewed by the Principal Investigator and other trained members of the research team in order to assess fidelity to administering the protocol. If a personnel's average fidelity rating drops below 85%, they will be temporarily prohibited from administering further CRP sessions until remedial training has been completed and they obtain fidelity ratings of at least 85% for three consecutive practice administrations of the CRP.

3.8 Data Analysis. A linear mixed effects regression analysis with repeated measurements will be conducted to examine differences in suicide risk between Veterans in the clinician-administered and self-administered CRP conditions. Condition will be entered as the independent variable and outcome measures at baseline and each follow-up assessment will be entered as outcomes. These analytic procedures are consistent with previous trials examining the efficacy of the CRP (Bryan et al., 2017; Bryan et al., 2018).

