3.9. Safety Procedures. The intervention under study includes two iterations of Crisis Response Planning, an intervention with demonstrated efficacy in reducing suicidal ideation and distress. Therefore, we anticipate that both versions of the CRP will demonstrate similar effects in this proposed study. Additionally, the use of crisis response plans, safety plans, and regular follow-up assessments are widely-used strategies that have been associated with decreased suicide risk and are all included in the proposed research. During enrollment in the study, all participants, regardless of agreement to participate in both portions of the study, will provide their contact information (home address, telephone number, email address) and a telephone number for an alternate person that study personnel may contact in case of imminent suicide risk. Home addresses may be used to contact the participant's local emergency services in case of imminent suicide risk. If a subject reports suicidal ideation, or a research staff member becomes aware that the subject is at imminent risk to harm himself/herself, the following questions will be asked to clarify the nature of risk (and to identify those at imminent risk requiring consideration for hospitalization): (1) Do you have a plan for killing yourself and do you intend to act on the plan?; (2) Do you have a desire to kill yourself that you believe you might act on?; (3) Have you already taken steps to act on your plan? If so, what steps have you taken? Both iterations of the CRP, which is a recommended and empirically-supported strategy for reducing suicide risk, will include contact information for professional resources and crisis services, the National Suicide Prevention Lifeline phone number, and other local behavioral health clinics and emergency departments. These procedures have been used successfully by our research team in dozens of studies with acutely suicidal individuals, to include multiple clinical trials. All participants will be provided with contact information to use in case of crisis (National Suicide Prevention Lifeline, emergency services), regardless of whether individuals choose to participate in developing the CRP.

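### Do the three descriptions of the self- versus clinician-administered comparison (Sections 1, 2.1 and 3.9) leave the meaning of a null result undefined?

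*Combined protocol and SAP*

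**What the plan says.** The passages are all current text in the combined protocol and SAP.

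- **Section 1 (Objectives)** sets the self-administered Crisis Response Plan (CRP) against the clinician-administered one, calls the effectiveness preliminary, and states: "As the aim of examining the effectiveness self- and clinician-administered versions of the CRP is exploratory, no hypotheses are proposed". It adds that the results will inform best practice for giving the CRP.
- **Section 2.1** describes the research as "examining the efficacy of the intervention in reducing suicidal ideation, distress, and negative affect and increasing positive affect when compared to a self-administered version". Here the self-administered version is the comparator.
- **Section 3.9 (Safety Procedures)**, after noting that the CRP has demonstrated efficacy, says: "Therefore, we anticipate that both versions of the CRP will demonstrate similar effects in this proposed study".
- **Section 3.8 (Data Analysis)** plans a linear mixed model "to examine differences in suicide risk between Veterans in the clinician-administered and self-administered CRP conditions". It sets no equivalence or non-inferiority margin and no rule for reading a non-significant result.
- **Section 3.2 (Sample)** justifies 150 participants, 75 per arm, as giving high power "to detect medium-sized effects in all regression-based analyses", and concludes that "the proposed sample size is sufficiently powered for the proposed analyses", even with 20% attrition.

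**The concern.** Read in sequence, Sections 1, 2.1 and 3.9 seem to give one contrast three purposes: none stated, a test of efficacy, and an expectation of similarity. Suppose the arms do not differ significantly, as Section 3.9 leads one to expect. Section 2.1 then seems to support a statement that efficacy was not shown, and Section 3.9 a statement that the two versions work equally well. Section 3.8 tests only for a difference, and absence of a significant difference is not evidence of similarity.

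The choice of statement would matter. The results are meant to guide how the CRP is delivered to Veterans with suicidal ideation, and a bare p-value above 0.05 could be used to support self-administration when a modest deficit had not been ruled out.

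**Working it through.** **1. Does the stated power belong to the planned question?**

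From Section 3.2: N = 150, two equal arms, m = 7 daily measurements, a medium effect, moderate correlations, power .98-.99 (printed as β, but evidently power). Assumed, because the document gives no values: f = 0.25 (0.5 SD between arms), two-sided alpha 0.05, compound symmetry with correlation ρ of 0.4 to 0.5.

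For the between-arm effect averaged over the repeated measures, λ = N f² m / (1 + (m − 1)ρ), with 1 and N − 2 degrees of freedom.

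| N | ρ | λ | Power |
|---|---|---|---|
| 150 | 0.4 | 65.625 / 3.4 = 19.30 | 0.992 |
| 150 | 0.5 | 65.625 / 4.0 = 16.41 | 0.980 |
| 120 (20% lost completely) | 0.4 | 52.5 / 3.4 = 15.44 | 0.974 |
| 120 (20% lost completely) | 0.5 | 52.5 / 4.0 = 13.13 | 0.949 |

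The stated figure reproduces. It is power to detect a medium difference between arms, which matches both the limit written into Section 3.2 and the analysis in Section 3.8. Section 3.2 makes no statement about similarity.

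**2. Does the reversed comparator change the analysis?**

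Section 1 implies self minus clinician; Section 2.1 implies clinician minus self. In a model with a two-level condition term, swapping the reference level changes the sign of the coefficient. Its size, standard error, interval width and two-sided p-value stay the same.

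**3. Are the two readings of a null result opposed?**

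- Section 2.1: both arms receive a CRP and there is no untreated arm. A null result can therefore say only that clinician delivery was not shown to be better than self delivery. Reading it as a CRP without efficacy would treat the self-administered version as inert, although Section 3.9 introduces both versions as forms of an intervention with demonstrated efficacy.
- Section 3.9: the sentence gives an expectation, in a passage explaining why participants in either arm are protected. A null result would be compatible with it. Nothing says that similarity will be concluded.

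The two readings differ in strength, not in direction. Both describe no demonstrated difference between two versions of one intervention.

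**4. What would the ordinary output show?**

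As an illustration, take the seven-day post-CRP average in units of the single-day SD. Its variance is (1 + 6ρ)/7, which is 0.571 at ρ = 0.5. The standard error of the difference is √(4 × 0.571 / 150) = 0.123, so the 95% half-width is about 0.24 SD (0.27 SD at N = 120). Over ρ = 0.3 to 0.7 it is 0.20 to 0.28 at N = 150 and 0.23 to 0.31 at N = 120. An estimate near zero would thus rule out a medium deficit of 0.5 SD and would not rule out 0.2 SD. The interval itself shows what a null result supports, without a margin or a choice between Sections 2.1 and 3.9.

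This averaging is one simple reading. Section 3.8 enters baseline as an outcome too and names no time term, so the figures are not a forecast of the trial's own precision.

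**The case for a change.** The strongest case for a change is that the inconsistency is real and the remedy costs almost nothing. Section 2.1 reverses the comparator of Section 1 and uses the language of efficacy. Section 3.9 states an expectation about a contrast said to carry no hypotheses. Section 3.8 does not explicitly promise an estimate with its interval. One purpose statement and one sentence on interpretation would remove any room for a choice after the results are known.

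At ρ = 0.5, without baseline adjustment and with a true difference of zero, N = 150 would exclude a 0.3 SD deficit with probability only 0.68 and a 0.2 SD deficit with probability 0.36. A claim of similarity from a non-significant test would therefore be weakly supported.

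The wording mismatch stands, and so does the warning against such a claim. The probabilities, however, answer a non-inferiority question that the protocol does not ask, with margins it does not set and a model that is not clearly the one in Section 3.8. If condition is instead a main effect over all eight measurements with no difference at baseline, they become 0.57 and 0.29. They measure no defect in this plan. A sentence on interpretation would only record ordinary practice for an exploratory comparison.

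**Conclusion.** No change to the plan is called for. Sections 1, 2.1 and 3.9 are loosely aligned, but Section 1 states the objectives and governs: the comparison is exploratory. Following Section 3.8 for that aim gives a sound analysis, and the power statement in Section 3.2 is correct for the difference it refers to. The effect of the mismatch on any stated number, rule or analysis is nil.

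This rests on two assumptions. First, the analysts report the between-arm difference with its 95% confidence interval for each outcome, including negative affect, which Section 2.1 names and the PANAS-SF measures. Second, they do not present non-significance as similarity. Both are routine. If the sponsor later wished to claim that the versions are equivalent or that one is non-inferior, a margin fixed before the data are seen would be needed. The document makes no such claim. Bringing the wording of Sections 2.1 and 3.9 into line with Section 1 would be harmless tidying, with no statistical gain.
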